**Table 1: Features and Magnifications for Viewing**

[figure not shown]
Feature #	Magnification / Rationale		
	10x	20x	40x
Tissue level	Cellular level	Subcellular level	
1	Small artery	Reed Sternberg cell	Cilia
2	Psammoma body	Polymorph neutrophil	Eosinophil with granules
3	Keratin pearl	Plasma cell	Mitotic Figure
4	Granuloma	Goblet cell	Infiltrating or metastatic lobular carcinoma
5	Adipocyte	Macrophage	Osteoid Matrix
6	Gland	Foreign body giant cell	Intercellular bridges
7	Necrosis	Clear Cell (of renal cell carcinoma)	Hemosiderin
8	Cartilage	Myxoid stroma	Intranuclear inclusion
9	Duct	Muscle cell	Melanin pigment
10	Nerve	Calcification	Crystals

Thus, the required number of study slides is 21 study features x 3 organs/study feature x 6 FOV/organ = 378 slides, which include selected study features and selected FOVs (see Table 2). An additional 162 sham slides will also be included.

The overall study design and required number of slides with selected features and selected shams are shown in Figure 2. The same slides will be used for all three sub-studies.

**Table 2: Required Number of Slides with Selected Features and Selected FOVs**

Feature	Organ	Slides with Selected Feature and Corresponding FOVs
1	1	1-6
1	2	7-12
1	3	13-18
2	1	19-24
2	2	25-30
2	3	31-36
.	.	.
.	.	.
.	.	.
21	1	361-366
21	2	367-372
21	3	373-378

**Figure 2. Slide Selection**

### 3.1.1 Intra-Scanner Precision Sub-study

[figure not shown]
The precision for the intra-scanner sub-study will be based on the assessments from three reading pathologists' who will identify specific histologic features that they observe in TIFF images of the FOV obtained from three scans from three scanners during three readings sessions. The study is diagrammed in the first column of Figure 3.

### 3.1.2 Inter-Scanner Precision Sub-study

The precision for the inter-scanner sub-study will be based on the assessments from three reading pathologists' who will identify specific histologic features that they observe in TIFF images of the FOV obtained from one scan from each of three scanners during three readings sessions. The study is diagrammed in the second column of Figure 3.

### 3.1.3 Inter-Site Precision Sub-study

The precision for the inter-site sub-study will be based on the assessments from one reading pathologist at each of three sites. The reading pathologists will identify specific histologic features that they observe in TIFF images of the FOV obtained from one scan from the one scanner assigned to their site during one reading sessions. The study is diagrammed in the third column of Figure 3.

**Figure 3. Study Schema**

## 4. RANDOMIZATION AND BLINDING

To minimize bias due to recall of FOVs from previous reads, different Reading Pathologists (RPs; or Readers) will be used in the three different sub-studies.

### 4.1 Method of Assignment and Randomization

For the study, there are several levels of randomization:

- Assignment of slides to sets and FOV location (study-level randomization)
- Assignment of sets to scanners (sub-study level randomization)
- Assignment of scans (iterations) to rotation for reading sessions (sub-study level randomization)

#### 4.1.1 Study-level Assignment of Slides to Sets

A stratified randomization will be used to assign slides to one of three sets, separately for study features and sham features. The 378 study FOVs will be divided into three sets of 126 slides such that 42 slides are from

each magnification. To assure this, the following factors will be considered in the stratified randomization: FOV magnification (10x, 20x, 40x), Feature, and Organ within feature. The 162 sham FOVs will be similarly divided into three sets using the same stratification factors. These three sets will remain constant for all three sub-studies. The assignment of FOVs to sets will not be blinded. FOVs will be indexed, for linkage with sub-study randomizations, as a two-digit feature number, a two-digit magnification number, a one-digit organ number, and a 1-digit slide number, all separated by a dash (e.g., 01-10-1-5 refers to small artery-10x magnification-organ number 1- slide 5). Additionally, a 4-by-4 grid will be used to randomly determine the location of the feature in the FOV as shown below where the 1-1 cell represents the upper left grid (Cell 1) and the 4-4 cell represent the lower right grid (Cell 16).

1	2	3	4
5	6	7	8
9	10	11	12
13	14	15	16

#### **4.1.2 Intra-scanner Precision Sub-study Random Assignments**

This sub-study includes one site with three scanners (called scanner A, scanner B, and scanner C). The random assignments required for this study are described in general below and in detail in Section 4.1.2.1 and 4.1.2.2.

A random assignment of sets to order of scanning on the Scanners will be generated. To accomplish this, a random ordering of 'First' 'Second' 'Third', three times will be performed and merged with the assignment of sets to scanners for each reader.

The random assignment of sets to scanners is specific to each reader. To accomplish this, a 3-by-3 Latin Square will be utilized where rows refer to RPs and columns refer to Scanners.

Once the three scans are generated, these iterations from each scanner are then assigned to a reading session such that in each reading session, one scan (or iteration) from each scanner is included in each reading session. To accomplish this, a second 3-by-3 Latin Square will be utilized where the rows represent the iteration and the columns represent the reading session. Further, FOVs may be randomly rotated in 90-degree intervals to minimize bias due to recall of the FOV; in addition, the order of the FOVs to be displayed within each session may be randomly ordered.

##### **4.1.2.1 Assignment of Sets to Scanners**

The order of Set 1, then Set 2, and then Set 3 can be represented as 123; order of Set 2 then Set 3 then Set 1 can be represented as 231; and, the order of Set 3, then Set 1, then Set 2 can be represented as 312. These orders represent three rows of a 3 x 3 Table where the columns represent the Sets. Then this will create the Latin Square shown in Table 3.

**Table 3: Example of a Latin Square**

	Column 1	Column 2	Column 3
Row 1	1	2	3
Row 2	2	3	1
Row 3	3	1	2

Each number appears once in each row and column. The number refers to a set of 126 slides.

By definition, a 3-by-3 Latin Square has the property that the numbers 1, 2, 3 (or the letters A, B, C) are represented once in each column and one in each row. The above Latin Square is one of twelve (12) possible Latin Squares that can be generated from the numbers 1, 2 and 3. The 12 possible Latin Squares are given in Table 4.

**Table 4: List of All Possible 3-by-3 Latin Squares**

$\begin{bmatrix} 1 & 2 & 3 \\ 2 & 3 & 1 \\ 3 & 1 & 2 \end{bmatrix}$	$\begin{bmatrix} 1 & 2 & 3 \\ 3 & 1 & 2 \\ 2 & 3 & 1 \end{bmatrix}$	$\begin{bmatrix} 1 & 3 & 2 \\ 2 & 1 & 3 \\ 3 & 2 & 1 \end{bmatrix}$	$\begin{bmatrix} 1 & 3 & 2 \\ 3 & 2 & 1 \\ 2 & 1 & 3 \end{bmatrix}$
$\begin{bmatrix} 2 & 1 & 3 \\ 1 & 3 & 2 \\ 3 & 2 & 1 \end{bmatrix}$	$\begin{bmatrix} 2 & 1 & 3 \\ 3 & 2 & 1 \\ 1 & 3 & 2 \end{bmatrix}$	$\begin{bmatrix} 2 & 3 & 1 \\ 1 & 2 & 3 \\ 3 & 1 & 2 \end{bmatrix}$	$\begin{bmatrix} 2 & 3 & 1 \\ 3 & 1 & 2 \\ 1 & 2 & 3 \end{bmatrix}$
$\begin{bmatrix} 3 & 2 & 1 \\ 1 & 3 & 2 \\ 2 & 1 & 3 \end{bmatrix}$	$\begin{bmatrix} 3 & 2 & 1 \\ 2 & 1 & 3 \\ 1 & 3 & 2 \end{bmatrix}$	$\begin{bmatrix} 3 & 1 & 2 \\ 1 & 2 & 3 \\ 2 & 3 & 1 \end{bmatrix}$	$\begin{bmatrix} 3 & 1 & 2 \\ 2 & 3 & 1 \\ 1 & 2 & 3 \end{bmatrix}$

One of the 12 Latin Squares will be selected by random and the rows randomly assigned to a RP. For example, for the following selection,

$$\begin{array}{ccc} 2 & 3 & 1 \\ 1 & 2 & 3 \\ 3 & 1 & 2 \end{array}$$

there are 6 possible choices for assigning the rows to the 3 readers. The choices are shown in Table 5.

**Table 5: Possible Assignments of Latin Square Rows to Readers**

Pathologist	Choices for Assigning Each Combination to a Reader					
	1	2	3	4	5	6
Reader 1	231	231	123	312	123	312
Reader 2	312	123	231	231	312	123
Reader 3	123	312	312	123	231	231

One combination (the selected Latin Square) will be randomly chosen and assigned to readers. Suppose the selected combination is choice 2. Then combination 231 will be assigned to Reader 1, combination 123 will be assigned to Reader 2 and combination 312 will be assigned to Reader 3.

Once the combination is assigned to each reader, the three scanners will be assigned in such a way that the first number of the combination is assigned to Scanner A, the second number is assigned to Scanner B and the third number is assigned to Scanner C. For choice 2 the assignment of readers and scanners for the selected Latin Square is given in Table 6.

**Table 6: Assignment of Latin Square Columns to Scanners**

	Scanner A	Scanner B	Scanner C
Reader 1	2	3	1
Reader 2	1	2	3
Reader 3	3	1	2

The number refers to a set of 126 slides.

Once the sets are assigned to Scanners for a Reader, the given set will be scanned three times (called Iteration 1 [or Scan 1], Iteration 2 [or Scan 2], or Iteration 3 [or Scan 3]) on the specified Scanner, with at least six hours downtime between Iterations to ensure full cool down. The resulting scan can be indexed by the set number and iteration number as given in Table 7 for **Reader 1**.

**Table 7: Indexing of Iteration to Set or Scanner for Reader 1**

Scanner	Set	Iteration		
		Iteration 1	Iteration 2	Iteration 3
Scanner A	2	2.1 [Set 2, Iteration 1]	2.2	2.3
Scanner B	3	3.1	3.2	3.3
Scanner C	1	1.1	1.2	1.3

All 162 sham slides will be scanned once on Scanner A.

#### 4.1.2.2 Assignment of Iterations to Reading Sessions

Once the slides are scanned three times and the FOVs created, the resulting FOVs need to be randomly assigned to a reading session for each Reader. From the above scanner by iteration Table (Table 7), one of

the 12 possible Latin Squares listed in Table 4 can be selected to assign the set-specific iterations to the three reading sessions for a given reader. The random assignment is such that for a given reading session each reading set comes from a different scanner and a different iteration. Continuing the example from the previous section, one possible Latin Square is given in Table 8 for the three reading sessions for **Reader 1**.

**Table 8: Assignment of Iterations to Reading Sessions for Reader 1**

		Reading Session		
		1	2	3
Scanning Set	2	Scanner A, Iteration 1, (2.1) (n=126)	Scanner A, Iteration 3, (2.3) (n=126)	Scanner A, Iteration 2, (2.2) (n=126)
	3	Scanner B, Iteration 3, (3.3) (n=126)	Scanner B, Iteration 2, (3.2) (n=126)	Scanner B, Iteration 1, (3.1) (n=126)
	1	Scanner C, Iteration 2, (1.2) (n=126)	Scanner C, Iteration 1, (1.1) (n=126)	Scanner C, Iteration 3, (1.3) (n=126)
Total		378	378	378

Set1, set2, and set3 do not need to be equal, but they need to add up to 378 slides and each set should have equal number of slides from each of 3 viewing magnifications

In this example, the first reading session will include the first iteration from Set 2 (Scanner A), the third iteration from Set 3 (Scanner B), and the second iteration from Set 1 (Scanner C) for Reader 1. Per reading session, **54 different sham slides will be added to each reading session**. The set assignment for the sham slides described in Section 4.1.2.1 will be used to assign slides to reading sessions; this assignment is built into the randomization schedule.

Independently, each iteration of each FOV for each Reader will be randomly rotated for presentation during the reading session. This will be performed by randomly selecting one of the four possible rotations: 0° (no rotation), +90°, -90°, or 180° with replacement. Sham slides and slides associated with Iteration 1 will not be rotated. This randomization schedule will then be linked to the above assignment of iterations to reading sessions to obtain the final randomization. Additionally, the FOV presentation order within a session for a Reader will be randomly ordered.

Three (3) separate reading sessions will be performed by each of three reading pathologists, with a washout period of at least two weeks between reading sessions.

***The process described above for Reader 1 will be repeated for Readers 2 and 3. At the end, all 378 slides are scanned by each scanner and read by each reader.***

#### **4.1.3 Inter-scanner Precision Sub-study Random Assignments**

This sub-study includes one site with three scanners (called scanner A, scanner B, and scanner C). The random assignments required for this study are described in general below and in detail in Section 4.1.3.1 and 4.1.3.2.

The random assignment of sets to scanners is to determine the order of scanning on the Scanners. To accomplish this, a 3-by-3 Latin Square will be utilized where rows refer to Sets and columns refer to Scanners.

Once the scans from the three scanners are generated, these scanner-specific scans are then assigned to a reading session such that in each reading session, one scan from each scanner is included in each reading

session. To accomplish this, a second 3-by-3 Latin Square will be utilized where the rows represent the iteration and the columns represent the reading session. Further, FOVs may be randomly rotated in 90-degree intervals to minimize bias due to recall of the FOV; and, the order of the FOVs to be displayed within each session may be randomly ordered.

#### **4.1.3.1 Assignment of Sets to Scanners**

Similar to the Intra-scanner Precision sub-study, one of the 12 Latin Squares depicted in Table 4 will be randomly chosen to assign Sets of study FOVs to Scanners, say

2	3	1
1	2	3
3	1	2

For this selected Latin Square, the assignment of sets to scanners and the scanning order is depicted in Table 9. Reading across the row for a given set, Set 1 is scanned on Scanner C first, then on Scanner A and then on Scanner B. Alternatively, reading down the column for a given scanner, Set 2 is scanned first on Scanner A, followed by Set 1 and then by Set 3.

**Table 9: Order of Scanning Sets on Scanners**

	Scanner A	Scanner B	Scanner C
Set 1	Second	Third	First
Set 2	First	Second	Third
Set 3	Third	First	Second

All 162 sham slides will be scanned once on Scanner A.

#### **4.1.3.2 Assignment of Scans to Rotations and Reading Sessions**

Once the FOVs are created, the resulting FOVs need to be randomly assigned to a reading session and a determination made as to which rotation of the FOV to display ( $0^\circ$  [no rotation],  $90^\circ$ ,  $180^\circ$ , or  $270^\circ$ ) during the reading session. To accomplish the assignment to a reading session, a second 3-by-3 Latin Square will be utilized for each Reader where the rows represent sets, the columns represent the reading session, and the entries represent scanners, say.

3	1	2
1	2	3
2	3	1

For this selected Latin Square, the assignment of set from scanner to a reading session is depicted in Table 10. Reading across the first row, Set 1 scanned on Scanner C is read during Session 1, Set 1 scanned on Scanner A is read during Session 2, and Set 1 scanned on Scanner B is read during Session 3.

Alternatively, reading down the first column, Reading Session 1 contains Set 1 scanned on Scanner C, Set 2 scanned on Scanner A, and Set 3 scanned on Scanner B. Per reading session, **54 different sham slides will**

**be added to each reading session.** The set assignment for the sham slides described in Section 4.1.3.1 will be used to assign slides to reading sessions; this assignment is built into the randomization schedule.

**Table 10: Assignment of Scanner-Set Combinations to Reading Sessions for Reader 1**

		Reading Session		
		1	2	3
Set	1	3 (Scanner C) (n=126)	1 (Scanner A) (n=126)	2 (Scanner B) (n=126)
	2	1 (Scanner A) (n=126)	2 (Scanner B) (n=126)	3 (Scanner C) (n=126)
	3	2 (Scanner B) (n=126)	3 (Scanner C) (n=126)	1 (Scanner A) (n=126)
Total		378	378	378
Set1, set2, and set3 do not need to be equal, but they need to add up to 378 slides and each set should have equal number of slides from each of 3 viewing magnifications				

After generating Table 10 for Reader 2 and Reader 3 using the same procedure as for reader 1, then the set assignment for each scanner for a given reading session for a given reader can be summarized as shown in Table 11. As shown in the table, sets 1, 2, and 3 scanned on Scanner A, will be read by all 3 readers and similarly, sets 1, 2, and 3 scanned on Scanners B and C will be read by all 3 readers.

**Table 11: Slide Reading Schedule**

Reader	Reading Session	Scanner A	Scanner B	Scanner C
1	1	Set 2	3	1
1	2	1	2	3
1	3	3	1	2
2	1	1	2	3
2	2	2	3	1
2	3	3	1	2
3	1	3	1	2
3	2	2	3	1
3	3	1	2	3
Total scans read		1134	1134	1134

Once the FOVs are assigned to a reading session, then a determination will be made as to which rotation will be presented using the same approach as for the Intra-Scanner precision sub-study. Sham slides and slides associated with scanning order “First” will not be rotated. These two randomization schedules will be combined to link order of presentation with rotation; the randomizations will be produced for each Reader separately.

#### **4.1.4 Inter-site Precision Sub-study Random Assignments**

This sub-study includes three sites with one scanner each. The random assignments required for this sub-study are not as complex as for the intra- and inter-scanner sub-studies. For this sub-study, all slides are scanned once at each site. For each reader (1 per site), the order of presentation of the FOVs will be random. No sham slides will be included.

The order in which the sets will be presented to the Reader will be randomly determined. This approach ensures that after every 126 slides, each magnification has had an equal number of features read.

#### **4.2 Blinding and Unblinding**

The randomization schedules will be kept blinded to the extent possible. The assignment of slides then sets and the location of the FOV will be known to personnel involved in the study.

### **5. WITHDRAWAL OR DISCONTINUATION**

#### **5.1 Slide Withdrawal**

It is unlikely that slides will be withdrawn from the study after they satisfy inclusion and exclusion criteria. However, if during the trial, before all slides have been scanned, a slide somehow gets damaged or misplaced and cannot be used, or an inadvertent mix-up is discovered, this slide may be withdrawn from the study (or a sub-study) and a protocol deviation noted. If necessary, a replacement slide from a new case may need to be screened, enrolled and added into the study (or sub-study) in order to continue completing the required imaging to satisfy the overall number of features examined for the given sub-study, and thus the study.

If a sub-study has been completed, the new slide will only be included in the sub-study(ies) which have not yet completed. The new slide will need to be scanned, replacing the withdrawn slide.

#### **5.2 Pathologist Withdrawal**

If a reading pathologist is unable to complete study reads according to study schedules, a replacement pathologist may be selected.

For the intra-scanner (inter-scan) and inter-scanner sub-studies, because of how the slides are split across reading sessions, the replacement pathologist will need to re-read any **slides** read by the original pathologist such that the **three reading sessions of the same slide** are from the **same pathologist**.

For the inter-site sub-study, because slides are only read once, the replacement pathologist will need to re-read any slides read by the original pathologist.

*The primary analysis will not use any readings from the original/previous pathologist.*

### **6. STATISTICAL ANALYSIS**

To minimize bias due to recall of FOVs from previous reads, different reader pathologists will be used in the 3 different sub-studies.

#### **6.1 Pathologist Experience**

Reader information (years of experience post-residency, categorized average number of cases per year [ $<5,000$ ,  $5,000$  to  $10,000$ ,  $>10,000$ ]) will be tabulated by sub-study and overall using descriptive statistics.

## 6.2 FOV Characteristics

The characteristics of the cases selected will be descriptively summarized using numbers and percentages by magnification and overall. The characteristics of the cases will include the features selected and the organ systems from which the features were selected.

## 6.3 Protocol Deviations

Protocol deviations will be listed by site, reader and sub-study. Additionally, the number and percentage of deviations will be summarized by site, reader and sub-study.

## 6.4 Intra-Scanner Precision Sub-study

To evaluate Intra-Scanner precision, the agreement rate of each reader for each scanner is first estimated, then averaged over all readers and scanners. Sham features are excluded from analysis. (see Section 4.1.2 for details of the randomization)

Each of three scanners will scan one-third of the slides three times; three Reading Pathologists (RPs; or Readers) will evaluate all FOVs across three reading sessions. Table 12 shows the number of comparison pairs for each scanner.

**Table 12: Intra-Scanner Pairwise Comparison**

Scanner	Number of Comparison Pairs
Scanner A	1134
Scanner B	1134
Scanner C	1134
Overall	3402

The number of comparison pairs is calculated based on three RPs where for each RP there are three pairwise comparisons, namely Iteration 1 vs. Iteration 2, Iteration 1 vs. Iteration 3, and Iteration 2 vs. Iteration 3. This results in 3 reader x 126 pairs per comparison x 3 pairwise comparisons =1134 (see Table 13) comparisons per scanner.

**Table 13: Number of Comparison Pairs per Scanner**

Reader	Number of Pairwise Comparisons			Total # of Pairwise Comparisons
	Iteration 1 vs. Iteration 2	Iteration 1 vs. Iteration 3	Iteration 2 vs. Iteration 3	
1	126	126	126	378
2	126	126	126	378
3	126	126	126	378
				1134

#### 6.4.1 Percent Positive Agreement

For a given scanner, the pairwise comparisons among Iteration 1, Iteration 2 and Iteration 3 can be displayed as three (3) 2x2 tables for a given reader. Table 14 demonstrates a 2x2 Table for the pairwise comparison of Iteration 1 versus Iteration 2 for Reader1 for Scanner A. The result of reading for each slide is “Yes” or “No” if the primary feature was detected correctly. Each primary feature shall be considered equally important as the next primary feature; thus, the results of all primary features will be pooled.

**Table 14: Agreement Table for Scanner A for Reader 1**

		Feature X is correctly identified in Iteration 2		
		Yes	No	
Feature X is correctly identified in Iteration 1	Yes	a	b	a+b
	No	c	d	c+d
		a+c	b+d	126

The nine (9) 2x2 tables for a given scanner will be pooled across the 3 readers to create one 2x2 Table (see Table 15) for the agreement between Iteration  $i$  and Iteration  $j$ , where  $i, j = 1, 2, \text{ or } 3; i \neq j; \text{ and, } j > i$ .

**Table 15: Agreement Table for Scanner A Across all Readers**

		Feature X is correctly identified in Iteration $j$		
		Yes	No	
Feature X is correctly identified in Iteration $i$	Yes	a 	b 	a  +b 
	No	c 	d 	c  +d 
		a  +c 	b  +d 	1134

Then the Percent Positive Agreement (PPA) can be estimated as  $a^1/1134$  for  $i = 1$  to 3, corresponding to Scanner A, Scanner B and Scanner C. Similarly, the results across all three scanners can be summed to obtain the overall PPA (see Table 16).

**Table 16: Intra-Scanner Results Across 3 Reading Pathologists for Each Scanner and Overall**

	Number of Pairwise Agreements	Number of Comparison Pairs	Agreement Rate %
Scanner A	a 	1134	(a  )/1134
Scanner B	a 	1134	(a  )/1134
Scanner C	a 	1134	(a  )/1134
Overall	a*	3402	(a*)/3402

To preserve the correlation structure of multiple readings of the same feature on an FOV, the bootstrap method will be used to derive a two-sided 95% confidence interval (CI) for the percent positive agreement. An FOV will be the bootstrap re-sampling unit.

The strategy in bootstrapping is to approximate the data generating mechanism (the data distribution function) using an empirical estimate. By design, the 378 study features are divided into 3 sets of 126 FOVs and each set is randomly assigned to a Scanner. Then 3 repeated scans (iterations) for each FOV and within each scanner are created for evaluation by each Reader. Since sets of FOVs are nested within scanners in this study, for bootstrap resampling the 3 scanners will be chosen **without** replacement (i.e., the same scanner cannot be sampled more than once).

After all data are collected, the database is cleaned and locked, the following data generation mechanism will be followed to preserve the correlation structure in this sub-study.

- a. Choose 3 scanners **without** replacement (because each reader should read 378 FOVs (126 FOVs per scanner)
- b. For each scanner, choose 126 FOVs **with** replacement from each set assigned to that scanner.
- c. Identify the reader for each of the selected FOV-scanner combinations.
- d. For each FOV-scanner-reader combination, calculate the within RP agreement status between reading sessions (1, 2), (1, 3), and (2, 3).
- e. Estimate overall intra-scanner percent positive agreement using the sampled data.
- f. Repeat step a to step e at least 1000 times to estimate a two-sided 95% confidence interval for the percent positive agreement.

Note: when the estimated agreement rate is at extreme values such as 0% or 100%, the arcsine variance transformation approach, using the Anscombe correction for the continuity will be used to calculate the 95% confidence interval instead of using the bootstrap.

The study's acceptance criterion for percent positive agreement is 85%. The lower limit of the 95% CI for the percent positive agreement will be compared to 85%. If the lower limit is greater than 85%, then the study will have demonstrated intra-scanner precision.

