 - Slides are selected from cases in a consecutive manner starting with cases at least one (1) year old since accessioning
 - Slide is a glass cover-slipped surgical pathology slide of human tissue
 - Slide stained with H&E or other stains
 - Slide has one of the designated primary feature in the FOV, which is readily observable in its natural environment although the slide may also have one or more secondary features from the same magnification group in the same FOV
 - Slide is available in the archives for use, or purchased commercially, is not damaged, has tissue on the slide which is still in good condition, has a stain that is not faded and otherwise passes all quality checks
- Exclusion criteria:
 - Slide is unable to be scanned, contains damaged tissue or has indelible markings
 - Slide comes from an active (less than 1 year old) case
 - Slide is from a patient who already has a slide enrolled in the study, only 1 slide per patient to be enrolled

DEVICE DESCRIPTION

Hamamatsu S360MD NanoZoomer Slide Scanner Digital Pathology System (NanoZoomer) is an automated digital slide creation, viewing, and management system. The Hamamatsu NanoZoomer S360MD Digital Slide Scanner creates diagnostic quality WSI digital images of glass slides containing formalin-fixed paraffin embedded (FFPE) tissue. Each image typically contains billions of image pixels, creating a digital image of the tissue on the original glass slide. The NanoZoomer captures digital images of entire slides for duplication, annotation, storage, retrieval, image sharing and viewing to permit the pathologist to make a primary diagnosis without needing to view those glass slides through a light microscope.

STATISTICAL METHODS

1. Intra Scanner Substudy

Each of 3 scanners will scan one-third of the slides 3 times for each reader (in such a way that at the end of this sub-study, all 378 study slides will be scanned by each scanner three times and all 378 slides will be evaluated by each reader, details are given in section 8.1). Three reading pathologist will evaluate all scanned slides across 3 reading sessions. In addition to 378 study FOVs selected, 162 “sham” FOVs of the different features will be selected per the same inclusion and exclusion selection criteria and inserted into the reading of slides battery to minimize or avoid bias by the reading pathologist, but the results of sham readings will not be included in any analysis.

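### As naturally read, the SAP 6.4.1 bootstrap steps resample the three readers of one FOV independently, so the deciding intra-scanner interval is not the FOV-unit interval the SAP declares; whether it is too narrow is not established

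*SAP*

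**What the plan says.** SAP 6.4.1 gives the purpose of the bootstrap as keeping the correlation of repeated readings of a feature on one FOV (Protocol 8.1.2 has the same aim) and states: "An FOV will be the bootstrap re-sampling unit". It justifies the algorithm with "Since sets of FOVs are nested within scanners in this study". Step b then takes, scanner by scanner, 126 FOVs with "replacement from each set assigned to that scanner". Step c is "Identify the reader for each of the selected FOV-scanner combinations". Step d scores the three session pairs within that reader. The lower limit of the resulting interval is compared with 85% and settles the sub-study.

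The allocation is described elsewhere. SAP 4.1.2 makes the set-to-scanner assignment different for each reader, with Table 6 as the worked example. The Protocol synopsis says that by the end "all 378 study slides will be scanned by each scanner three times and all 378 slides will be evaluated by each reader".

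Other wording in SAP 6.4 and 6.4.1 suggests different layouts. One phrase in 6.4.1 is "each set is randomly assigned to a Scanner". Section 6.4 has "Each of three scanners will scan one-third of the slides three times", without the Protocol synopsis's qualification that this holds for each reader. On what the readers are shown, 6.4.1 has: "Then 3 repeated scans (iterations) for each FOV and within each scanner are created for evaluation by each Reader".

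**The concern.** If the FOV is the unit, a drawn FOV should bring all its reads with it: three readers, each with three iterations. The written steps attach only the one reader who saw that FOV on that scanner. The other two readers' results for the same FOV belong to the other two scanners and are drawn separately. Any tendency of an FOV to be easy or hard for all readers then drops out of the interval.

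The only pass/fail rule of the sub-study rests on this interval. The programmer would also have to choose between layouts that the SAP text does not reconcile, possibly with data in hand. The intervals in 6.4.2 come from the same bootstrap and those in 6.4.3 repeat the steps, but neither carries an acceptance criterion.

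**Working it through.** **1. The plan's count.** 21 features x 3 organs x 6 FOVs = 378 FOVs. Per scanner, 3 readers x 126 x 3 iteration pairs = 1134; over three scanners, 3402. SAP Table 12 is reproduced.

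**2. The layout in SAP Table 6, rearranged by set.**

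| | Scanner A | Scanner B | Scanner C |
|---|---|---|---|
| Set 1 | Reader 2 | Reader 3 | Reader 1 |
| Set 2 | Reader 1 | Reader 2 | Reader 3 |
| Set 3 | Reader 3 | Reader 1 | Reader 2 |

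Every scanner has all three sets, and each of the nine cells has exactly one reader. Sets are nested in scanners only within one reader; over readers they are crossed.

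**3. What the steps can mean.**
- A separate draw for each scanner and each set assigned to it: 9 x 126 x 3 = 3402 pairs. It runs, and is the natural reading of steps b and c, but the three readers of an FOV are drawn independently.
- One set per scanner: 3 x 126 x 3 = 1134 pairs, not 3402.
- Each FOV on one scanner only, read there by all three readers: 3 x 126 x 3 x 3 = 3402, but it cannot be run, because each FOV-scanner pair has one reader.
- One draw per set, reused on all scanners: 3 x 126 x 9 = 3402 with the FOV kept whole. It runs, but the text does not state it.

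**4. Written against declared standard error (SE).** Let s2 be the variance of one reader's score on one FOV, and rho the correlation of two readers' scores on the same FOV. There are 378 x 3 = 1134 such scores, each from three pairs.
- Written steps: variance s2/1134.
- FOV as unit: variance s2(1 + 2 rho)/1134.
- SE ratio: 1/sqrt(1 + 2 rho) = 1/sqrt(1.2), 1/sqrt(1.6), 1/sqrt(2.0) = 0.91, 0.79, 0.71 at rho 0.1, 0.3, 0.5.

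The documents give no rho; these values are assumptions.

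**5. Written against true SE.** This depends on whether the 21 features are fixed, as SAP Table 1 and the feature-stratified allocation in SAP 4.1.1 suggest. False-pass rates below are at a true PPA of 85%, from simulation (5000 trials per row, 1000 percentile replicates, probit model with FOV and FOV-by-reader effects, plus 21 fixed feature effects in the fixed rows). The Monte Carlo SE is 0.1 to 0.4 points.

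| Frame | Written SE / true SE | SAP steps | FOV drawn within set | FOV drawn within feature |
|---|---|---|---|---|
| Features fixed, total rho 0.30, within-feature rho 0.03 | 1.14 | 1.6% | 0.3% | 3.3% |
| same, within-feature rho 0.13 | about 1.0 | 3.1% | 1.1% | 3.5% |
| same, within-feature rho 0.24 | 0.86 | 6.1% | 2.5% | 4.0% |
| Features not fixed, rho 0.1 | 0.91 | 4.2% | 3.1% | not run |
| Features not fixed, rho 0.3 | 0.79 | 7.1% | 3.4% | not run |
| Features not fixed, rho 0.5 | 0.71 | 9.3% | 3.3% | not run |

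**6. Why no break-even rule is offered.** Scale total variance to 1, with shares F (feature), W (FOV within feature) and G (feature-by-reader), and rho = F + W = 0.30. With features fixed, the true variance is proportional to 1 - F - G + 2W and the written one to 1, so they are equal when 2W = F + G.
- G = 0: W = 0.10, F = 0.20, within-feature rho = 0.10/0.80 = 0.125.
- G = 0.10 (assumed): W = 0.133, F = 0.167, within-feature rho = 0.133/0.733 = 0.18.

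The crossing point moves with G, which the documents do not give.

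**7. Reach.** Without fixed features, the median observed PPA needed to pass at rho 0.3 is 86.8% under the written steps and 87.3% with the FOV as unit. Solving p - 1.96 x SE = 85% with s2 = p(1 - p) gives 86.96% and 87.44%. The decision differs only in a band of about half a point.

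**The case against.** Several points on the other side stand.

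- Step b does draw FOVs, and step d keeps one reader's three iterations together. It would be too strong to infer that the bootstrap ignores repeat readings; only the between-reader covariance is lost.
- A reader might infer that no workable version of the text keeps the FOV whole. One draw per set reused on every scanner does so, and step b does not expressly say the draws are independent. But its scanner-by-scanner instruction and the nesting sentence point away from that version, so it has to be written down.
- A reader might infer that the written interval is too narrow and the sub-study too easy to pass. The documents do not support this. With features fixed, the written steps are conservative, near nominal or liberal according to quantities not given. Feature-by-reader differences, such as one pathologist missing one feature, push towards conservatism.
- The declared FOV draw within set can itself be quite conservative with fixed features (0.3% to 2.5% above). The draw within feature runs above 2.5%.
- Eligible features must be readily seen (Protocol 5.2.1) and are confirmed by a second pathologist (Protocol 7.4), which may keep rho low.

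These points limit the size and direction of the effect. They do not remove the mismatch between the declared unit and the written steps.

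**Conclusion.** The conflict is established from the documents alone. SAP 6.4.1 declares an FOV-unit bootstrap and describes a nested layout; Section 4.1.2 and the Protocol synopsis describe a crossed one; and steps b and c, naturally read, do not deliver the declared interval. Whenever rho is positive the written SE is smaller than the declared one, by the factor in step 4 of the working.

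Against the true SE, no direction and no proven rise in false passes is claimed: both turn on rho, on feature-by-reader differences and on whether features are fixed. The practical reach is narrow, and the estimate a*/3402 does not change. The algorithm should be corrected before analysis because it produces the deciding limit, but the evidence does not make it a condition of the trial's validity. Severity: should fix.

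**What to change.** - **SAP 6.4.1:** within each set draw 126 FOVs with replacement once; carry all nine reads of each drawn FOV (3 readers on their assigned scanners x 3 iterations), as the inter-site algorithm in 6.6.1 does with its readers; compute a*/3402. Reword the nesting sentence: sets are nested in scanners within a reader and crossed with scanners over readers.
- **SAP 6.4.3:** make the same change with 36 FOVs per set (3 x 36 x 9 = 972 pairs).
- **SAP 6.5.3 and 6.6.3**, which import that method: draw per set and carry all reads of each drawn FOV.
- **Before analysis**, state that the draw within set may be conservative if features are treated as fixed. A draw within feature (18 FOVs each, all nine reads carried) can be a sensitivity analysis, rescaled because its SE is low by sqrt(17/18) = 0.97.

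Cost: wording and a few lines of code, no new data. The primary interval widens by sqrt(1 + 2 rho): 1.10, 1.26 and 1.41 times at rho 0.1, 0.3 and 0.5. In simulation without fixed features at rho about 0.3 (2500 trials per value), the chance of passing falls from 85.7% to 74.1% at a true PPA of 88%, from 98.2% to 94.6% at 89%, and from 99.9% to 99.8% at 90%.
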